### Sample/Participants

The research coordinator will perform chart review on Emergency Department patients presenting with chest discomfort. If there are 2 sets of troponins ordered and no exclusion criteria then the research coordinator will approach the patient for consent.

Inclusion criteria: Adult Emergency Department patients undergoing 0 and 2 hour troponin testing who have been administered aspirin within 30 minutes of the initial blood draw. Initially all patients undergoing this testing will be candidates for the study. We will attempt to enroll 80 patients in the each of the 3 arms. Determination of which (if either) narcotic is administered will be up to the clinician. As we reach the enrollment goals our research coordinator will discuss with the clinicians the expected pain plan to tailor enrollment of patients in the treatment arms that are still needed

Exclusion criteria: Patients not expected to get a 2 hour troponin; patients already on aspirin, clopidogrel, or stronger anti-coagulants; patients who arrived via EMS given it can be difficult to find the run reports to determine whether patient received fentanyl in the pre-hospital period; pregnant patients; patients on chronic narcotics; patients already once enrolled in this study, inability to provide consent in English

With regards to at risk populations, Economically Disadvantaged, Nursing home residents, prisoners, homeless patients are all commonly encountered in the ED. However, the request of 1 or 2 blue top tubes (totaling about a teaspoon of blood) is not an onerous ask. Since narcotic use (or non-use) will be wholly up to the provider and not impacted by this study we see no problems with including them.

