#### **Research Design**

Patients who have 0 and 2 hour troponins ordered will have their chart reviewed by the research coordinator for candidacy in the study (see below for inclusion/exclusion). If the patient meets study entry criteria then platelet aggregation studies using arachidonic acid will be added on to the 0 and 2 hour lab draw.

The study will compare the 0 and 2-hour platelet aggregation scores of patients receiving aspirin who are undergoing two sets of troponin tests. The first group will consist of patients not receiving any narcotics, the second group will include those receiving morphine, and the third group will include those receiving fentanyl. The treating clinician will determine the appropriate pain treatment plan for each patient.

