#### Instrumentation-Data collection

If consent is given to obtain the labs then the research coordinator will extract basic demographic information into a spreadsheet (name, MRN, age, sex, race, ethnicity), as well as the results of the labs including the CBC data already obtained (hemoglobin and platelet count). We will record the patients' creatinine to also help describe our population. Finally the platelet aggregation data that we are studying will be recorded, as well as confirmation with the patient that they are not on anti-platelet medicines such as aspirin, clopidogrel (Plavix), aspirin-dipyridamole (Aggrenox), prasugrel (Effient), ticagrelor (Brilinta). We will record time and dosing of aspirin administration, time and dosing of narcotic medicines (morphine, fentanyl, dilaudid).

This spreadsheet would be maintained on SH-Lakeland servers in a location only accessible to the research coordinator and PI.

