# **Data Analysis Procedure**

In the PACIFY trial, at 2 hours, patients receiving fentanyl had a PRU value of 113 +/- 94 on the platelet aggregation study (light aggregometry using ADP) after receiving Brilinta (ticagrelor), versus 71 +/- 66 in those not receiving fentanyl. With an alpha of 0.05 and beta of 0.8, 57 patients would be required to demonstrate statistical significance if there is a similar magnitude of effect. In the PERSEUS trial at 2 hours, patients receiving fentanyl had a PRU value of 173 +/-90 after also receiving Brilinta (ticagrelor), versus 210 +/- 76 in those receiving morphine and Brilinta (ticagrelor). 74 patients would be required to show statistical significance in direct comparison of morphine vs fentanyl. The aim is to enroll 80 patients in each arm (no narcotic, morphine, and fentanyl).

Two-tailed T-testing will be used to look for differences in the 2 hour platelet reactivity response rates between those receiving morphine versus those not receiving narcotics and between those receiving fentanyl and those not receiving narcotics.

If the data is sent to the Spectrum Health SASS team for analysis MRN's will be converted to a study ID so that the actual MRN will not be sent out.

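### The aspirin window has no stated direction, and the planned t-tests make no stated use of aspirin timing or the 0-hour aggregation value in non-randomised groups

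*Combined protocol and SAP*

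**What the plan says.** - **Timing of aspirin.** Sample/Participants includes patients "who have been administered aspirin within 30 minutes of the initial blood draw". It gives no direction.
- **Sampling.** Under Research Design, "platelet aggregation studies using arachidonic acid will be added on to the 0 and 2 hour lab draw". No tolerance around the second draw is given.
- **Comparison described in the design.** Research Design also states: "The study will compare the 0 and 2-hour platelet aggregation scores of patients receiving aspirin".
- **Group membership.** Sample/Participants: "Determination of which (if either) narcotic is administered will be up to the clinician". There is no randomisation.
- **Data recorded.** Instrumentation-Data collection: "We will record time and dosing of aspirin administration, time and dosing of narcotic medicines (morphine, fentanyl, dilaudid"). The actual draw times are not among the items listed.
- **Analysis.** The Data Analysis Procedure is the only analysis text: "Two-tailed T-testing will be used to look for differences in the 2 hour platelet reactivity response rates". It covers morphine versus no narcotic and fentanyl versus no narcotic. It names no covariate, change score or time term, and does not define the response rate.

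**The concern.** The background section rests the hypothesis on opioids slowing the absorption of oral drugs. The 2-hour aggregation value is then one point on a curve that may still be moving, and minutes since aspirin help decide where on it a patient sits. If one group receives aspirin later relative to its draws, it can look less inhibited at 2 hours even when its narcotic does nothing. That would mimic the hypothesised effect, and an imbalance in the other direction would hide a real one. An unadjusted t-test cannot separate the two, and a larger sample does not remove the bias.

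The 0-hour value raises a similar issue. In clinician-chosen groups, starting aggregation may differ, and a comparison of 2-hour values alone would read that difference as a drug effect. It would also give up precision from a measurement the study already takes.

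Finally, Research Design and the Data Analysis Procedure do not clearly describe the same outcome. Unless this is settled beforehand, the choice between raw 2-hour values, change and adjusted values could be made after seeing the data.

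**Working it through.** **1. The plan's own figure.** For fentanyl versus no narcotic, the Data Analysis Procedure takes 113 (SD 94) and 71 (SD 66) from a cited ticagrelor trial, a difference of 42. It says: "With an alpha of 0.05 and beta of 0.8, 57 patients would be required to demonstrate statistical significance". Read the stated beta as power of 0.80. Per-arm n = 2(1.960 + 0.842)² × SD² / difference².
- SD as the simple mean, (94 + 66)/2 = 80: n = 57.0, which reproduces 57 as a per-arm number.
- SD as the root mean square, √((94² + 66²)/2) = 81.2: n = 58.7, so 59.

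**2. Aspirin-to-sample interval**, with the second draw exactly 120 minutes after the first.
- Aspirin before the draw only: 120 + 0 to 120 + 30 = 120 to 150 minutes.
- Either side: 120 − 30 to 120 + 30 = 90 to 150 minutes.

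Any departure from exactly 120 minutes between draws changes these limits.

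**3. Bias from a timing imbalance.** With 80 per arm, SE = √((94² + 66²)/80) = 12.84. Bias b = slope × difference in mean interval. The rejection rate with no drug effect is Φ(b/SE − 1.96) + Φ(−b/SE − 1.96). The slope and the 10-minute imbalance are assumptions; the documents give neither.

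| Slope (units/min) | Bias at 10 min | Share of 42 | Rejection rate |
|---|---|---|---|
| 0 (plateau) | 0 | 0% | 5.0% |
| 0.25 | 2.5 | 6% | 5.4% |
| 0.5 | 5.0 | 12% | 6.8% |
| 1.0 | 10.0 | 24% | 12.2% |

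**4. Timing that varies but is balanced.** A uniform 60-minute spread has SD 60/√12 = 17.3 minutes. At 1 unit per minute the outcome SD becomes √(81.2² + 17.3²) = 83.0, and n rises from 59 to 62 per arm. The loss of precision is small; the exposure is to imbalance.

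**5. Precision from the 0-hour value.** Residual SD = 81.2 × √(1 − ρ²), where ρ is the correlation between 0-hour and 2-hour values (assumed). Power is for a difference of 42, 80 per arm, two-sided 5%, noncentral t.

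| ρ | Residual SD | Power |
|---|---|---|
| 0 | 81.2 | 90.2% |
| 0.3 | 77.5 | 92.6% |
| 0.5 | 70.3 | 96.4% |
| 0.7 | 58.0 | 99.5% |

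Fentanyl versus no narcotic is used because it is a listed test with planning figures. Morphine versus fentanyl is sized but has no listed test, and morphine versus no narcotic has no planning figures.

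**The case against.** **The wide interval is not established.** A reader might infer that aspirin can fall on either side of the draw and that the interval therefore runs from 90 to 150 minutes. The criterion does not say so. Its wording also fits aspirin before the draw only, which halves the range. This stands, and the point is confined to the missing direction.

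**The plan may not discard the 0-hour value.** A reader might infer that only raw 2-hour values will be analysed. The response measure is undefined, and read with Research Design it could mean change from the 0-hour value. This also stands. What can be said is that the two sections do not clearly agree and that no use of the 0-hour value is stated in the analysis.

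**The magnitudes have no source in the documents.** Slope, imbalance and correlation are all assumed. A slope of 1 unit per minute across 60 minutes is 60 units, more than the planning effect of 42, so the upper end is generous. The SDs are ticagrelor platelet-reactivity values, whereas this study measures arachidonic-acid aggregation after aspirin, so the units may not carry over. This stands, and the figures are illustrations only.

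**The 0-hour value may itself be affected by treatment.** A tube drawn after aspirin or a narcotic could carry part of the effect, and adjusting for it could absorb some of the difference sought. This stands as a real cost of adjustment.

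None of these objections supplies a stated use of the recorded aspirin time in the analysis, or anything that would balance timing across clinician-chosen groups.

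**Conclusion.** The concern holds in this limited form: the direction of the 30-minute window is unstated, the outcome is not clearly defined, and the only planned analysis is unadjusted in non-randomised groups although the aspirin time and both aggregation values are to be collected. The documents do not show that timing differs between groups, that the result will be biased, or that the error rate will reach 12.2%. That figure needs both a 10-minute imbalance and a slope of 1 unit per minute. With a plateau the error stays near 5%, and with balanced timing the loss of precision is small. Nor is the study shown to be underpowered for fentanyl versus no narcotic: on the plan's own inputs, power is already 90.2%. Baseline adjustment adds about 2 points at a correlation of 0.3, about 9 at 0.7, and nothing near zero. The case for change is that protection against a plausible bias, and possibly some precision, can be had almost free. It should be made, but it does not invalidate the design.

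**What to change.** 1. **Sample/Participants:** state whether the 30-minute window runs before the 0-hour draw, after it, or both.
2. **Data Analysis Procedure:** define the outcome as 2-hour arachidonic-acid aggregation. Replace the t-tests with one linear model on group (three levels), adjusted for 0-hour aggregation and minutes from aspirin to the 2-hour draw, with standard errors robust to unequal variances. Report the two planned contrasts from it.
3. **Research Design:** reword the comparison so that it matches that analysis.
4. **Instrumentation-Data collection:** add the actual times of both draws beside the aspirin and narcotic times.
5. **Sensitivity analysis:** repeat the model in patients whose 0-hour tube was drawn before both aspirin and any narcotic, using the recorded times. If the window is defined as aspirin before the draw only, this subset is empty; in that case, report the model with and without the 0-hour value.

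The cost is plan wording and two time stamps per patient, with no extra patients, blood or change in care. The downside is that a 0-hour value taken after aspirin or a narcotic may absorb part of the effect. The sensitivity analysis shows how far that matters but cannot recover clean baselines that were never drawn. Adjustment also does not remove other differences between clinician-chosen groups.

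### Closing arms as they fill can leave the groups partly non-concurrent, the unadjusted 2-hour t-tests cannot correct for that, and nothing shields prescribing from the recruitment conversation

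*Combined protocol and SAP*

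**What the plan says.** Treatment is not randomised. Research Design states: "The treating clinician will determine the appropriate pain treatment plan for each patient". Sample/Participants repeats this: "Determination of which (if either) narcotic is administered will be up to the clinician".

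Sample/Participants then sets out two phases of enrolment. In the first, all groups are open: "Initially all patients undergoing this testing will be candidates for the study". The target is equal numbers: "We will attempt to enroll 80 patients in the each of the 3 arms". The second phase starts as targets are approached, when the coordinator is to "discuss with the clinicians the expected pain plan to tailor enrollment of patients in the treatment arms that are still needed".

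The same section, when justifying the inclusion of at-risk populations, says that narcotic use is "wholly up to the provider and not impacted by this study".

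Data Analysis Procedure plans two-tailed t-tests on the 2-hour response, each narcotic group against no narcotic, with no covariates. Research Design does provide a 0-hour aggregation sample for every patient, but the planned test does not use it. The items listed under Instrumentation-Data collection include the times of aspirin and narcotic administration; enrolment date is not named as an item.

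**The concern.** Two separate issues arise from the same enrolment rule.

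**Calendar time.** An arm that fills early closes while the others continue. Patients recruited afterwards to the slower arms are then compared with patients from an earlier period. Changes over that time in assay performance, reagents, staff, case mix or prescribing habits would fall unequally on the groups. A plain t-test has no means of separating such a change from an effect of morphine or fentanyl.

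**The conversation about the expected plan.** It concerns an expected plan, so it can take place before treatment is given. Nothing requires the decision to be made or recorded first, and nothing keeps the clinician from learning which arm still needs patients. The statement that the study does not affect narcotic use is therefore an assertion with no procedure behind it. It also carries weight outside the statistics, because it is the stated reason for including prisoners, nursing home residents and homeless patients.

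**Working it through.** The plan gives no figure for either issue, so what follows is a sensitivity illustration. It uses the plan's own planning SDs; everything else is labelled as assumed.

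**Inputs from Data Analysis Procedure.** Fentanyl 113, SD 94; no fentanyl 71, SD 66; difference 42; two-sided alpha 0.05; 80 per arm. The stated beta of 0.8 is read as power of 0.80. The SDs are PRU values after ticagrelor. This study measures arachidonic-acid aggregation after aspirin, so the units are borrowed.

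**The plan's own figure, to confirm the inputs.** With the simple mean of the two SDs, (94 + 66)/2 = 80:

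n = 2 × (1.960 + 0.842)² × 80² / 42² = 57 per group, which matches the stated 57, read as per group. The root-mean-square SD of 81.2 gives 59.

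**Step 1: how far apart in time the groups can be.** Assume a constant flow of eligible patients. An arm with share s fills after 80/s eligible patients. If the no-narcotic arm fills at fraction f of the accrual period and the slowest arm at 1, mean enrolment times are f/2 and 1/2, so the gap is (1 − f)/2 of the period.

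| Assumed shares (none / morphine / fentanyl) | Fill points | f | Gap in mean enrolment time |
|---|---|---|---|
| 34 / 33 / 33% | 235 vs 242 patients | 0.97 | 0.015 |
| 60 / 20 / 20% | 133 vs 400 patients | 0.33 | 0.333 |
| 80 / 10 / 10% | 100 vs 800 patients | 0.125 | 0.438 |

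**Step 2: from drift to a false difference.** Assume a linear drift of D units over accrual and no true narcotic effect. The spurious difference is D × gap. At a gap of one third, D = 15, 30 or 45 gives 5, 10 or 15 units.

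**Step 3: false-positive rate.** SE = √((94² + 66²)/80) = 12.84. With shift b, the two-sided rejection rate is 1 − Φ(1.96 − b/SE) + Φ(−1.96 − b/SE).

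| Shift b | b/SE | Rejection rate with no true effect |
|---|---|---|
| 0 | 0 | 5.0% |
| 5 | 0.39 | 6.8% |
| 10 | 0.78 | 12.2% |
| 15 | 1.17 | 21.5% |

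Under near-equal shares, even D = 45 gives a shift of only 45 × 0.015 = 0.7 units, and the rate stays at 5.0%.

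**Scale-free version.** Because the units are borrowed, the same calculation in SD units is useful. With 80 per arm, SE = √(2/80) = 0.158 SD. A group difference of 0.1, 0.2 or 0.3 SD from drift or selection gives about 9.7%, 24% or 48%.

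**The conversation.** No arithmetic applies. The text says that enrolment is tailored and that the clinician decides. It does not say that the clinician's decision precedes the discussion, or that the clinician is kept unaware of which arms are open.

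**The case against.** The strongest reply has four parts.

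1. *The rule tailors enrolment, not prescribing.* The coordinator may simply ask what the clinician intends and then decide whether to approach the patient. This stands. A reader might infer that clinicians are told which drug the study needs, or that the protocol contradicts itself by claiming "narcotic use (or non-use) will be wholly up to the provider and not impacted by this study". The documents support neither reading. What they show is a missing safeguard.

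2. *The groups overlap.* All three open together, and non-concurrence appears only if fill rates differ. This also stands: a reader might infer that the rule necessarily makes the groups non-concurrent, but the fill point runs from about 12% to 97% of accrual under the assumed shares above. That the no-narcotic arm fills first is plausible but is not stated.

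3. *The illustration is weakly anchored.* The SDs come from another drug and another platelet trigger, and a 45-unit drift exceeds the whole planning difference of 42. This stands as a limit on the figures, which should not be read as an estimate. In addition, purely additive assay drift would shift the 0-hour and 2-hour samples alike and cancel in the within-patient change. The planned test, however, uses only the 2-hour value.

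4. *Clinician-chosen treatment is confounded by indication in any case.* True, and probably the larger problem. It does not excuse a second source of bias that can be reduced cheaply, and of which the concurrency part can be prevented only while enrolment is running.

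**Conclusion.** The point holds in a conditional form. Followed as written, the enrolment rule can leave later patients in slow arms without contemporaries in a filled arm, and the planned analysis has no term for calendar time or baseline to absorb the consequence. How much this matters cannot be determined from the documents. It is negligible if the arms fill at similar rates. On an assumed 60/20/20 split with an assumed linear drift of 15 to 45 units, it raises the false-positive rate from 5% to between about 7% and 22% per comparison.

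On the conversation about the expected plan, the conclusion is limited to this: the claim that the study does not affect narcotic use is unprotected. There is no evidence in the documents that drug choice is or will be altered.

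The plan should be changed because the remedy is cheap and works best during accrual. Later adjustment for date cannot supply contemporaries who were never enrolled, nor undo a drug choice if one had been prompted.

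**What to change.** **Sample/Participants.** Pace no-narcotic enrolment to the cumulative count of the slower narcotic arm, so that it stays open until both narcotic arms are complete. Keep 80 per arm. The cumulative count of the slower arm is the one to use. A monthly cap tied to the larger narcotic arm would not do: at an assumed 4 and 2 narcotic patients per month, no-narcotic could fill at month 20 (80/4) and the slower arm at month 40 (80/2). Mean enrolment times of 10 and 20 months would then leave a gap of a quarter of accrual.

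**Coordinator's procedure.** Take the clinician's plan from the chart, or ask for it only after it has been decided, and do not disclose which arms are open. An absent order does not by itself identify a no-narcotic patient, since an order may still follow. The analysis group should therefore be assigned by the narcotic actually given before the 2-hour draw. Who receives what remains entirely the clinician's decision.

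**Instrumentation-Data collection.** Add enrolment date.

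**Data Analysis Procedure.** Replace the plain t-tests with a regression of the 2-hour value on group, 0-hour value and enrolment date.

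**Cost.** Protocol wording, one more data item and a different order of approaching patients. The no-narcotic arm closes later and could be smaller if accrual stops early, and some patients will be missed.

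**What remains.** If one narcotic arm fills before the other, its mean enrolment date will still differ from that of the no-narcotic arm. Its patients will nevertheless have no-narcotic contemporaries, so the date term adjusts within overlapping periods. A direct morphine versus fentanyl comparison would keep some non-concurrence. Confounding by indication is not addressed by any of this.

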### Theoretical Framework-Present Knowledge, Literature Review

Patients experiencing heart attacks or unstable angina (commonly known as acute coronary syndrome (ACS)) commonly experience discomfort and pain. Nitroglycerin is typically the first medicine given for discomfort because it has dilatory effects upon vasculature to reduce the blood pressure and relax blood vessels to decrease myocardial demand. However, in some patients it is contraindicated and in many patients it is only partially efficacious in reducing discomfort. Narcotics are commonly given. Classically morphine was given in ACS as it is also thought to have venodilatory properties and could perhaps also relax the patient to decrease the sympathetic demands of the frightfight-flight responses experienced by patients having heart attacks. Narcotics have several common side effects, and one of these is decreased gastrointestinal (GI) transit time, commonly manifested as constipation. However, this decreased GI transit time also can slow the absorption of oral medications. Oral anti-platelet therapy (starting with aspirin and commonly including dual anti-platelet therapy with clopidogrel as well) is also part of the treatment of patients with ACS as reducing clot propagation in the coronary arteries can decrease the size of an infarct. Interference with oral anti-platelet therapy has been observed with morphine (2) contributing to worse outcomes in patients receiving morphine (1). Delayed onset of action or decreased absorption has also been demonstrated with stronger anti-platelet drugs such as clopidogrel (3) and prasugrel (4) in association with morphine. Many physicians have therefore switched to using fentanyl, and fentanyl has been found to be equally efficacious in pain control in potential ACS (7). The PACIFY trial (5) evaluated the effects of fentanyl upon the stronger anti-platelet agent ticagrelor and found statistical significance at 2 hours with a lower peak concentration, and delayed onset of the peak concentration of ticagrelor when fentanyl was given. The PACIFY trial did not compare the effects of morphine to fentanyl. The PERSEUS trial was a small study of 38 patients (6) which showed no difference between fentanyl and morphine at 2 hours with regards to ticagrelor absorption but that there was a difference at 4 hours. There has not to our knowledge been any study of fentanyl's effect on aspirin absorption.

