## **Research Questions or Hypothesis**

It is unlikely that a sufficient sample of patients with acute coronary syndrome (ACS) can be obtained to prospectively compare fentanyl to morphine, as the administration of other anticoagulants would confound the results. Therefore, the study will focus on chest pain patients in the emergency department. The hypothesis is that both morphine and fentanyl will reduce the effectiveness of aspirin.

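### Must the plan record and adjust for anticoagulants or second antiplatelets started in the emergency department before the 2-hour draw?

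*Combined protocol and SAP*

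**What the plan says.** All references are to the combined protocol and SAP.

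- **Research Questions or Hypothesis** explains why patients with acute coronary syndrome (ACS) are not the study population: "as the administration of other anticoagulants would confound the results". The study turns to emergency department chest pain instead.
- **Sample/Participants** excludes "patients already on aspirin, clopidogrel, or stronger anti-coagulants". It also excludes anyone in whom a second troponin at 2 hours is not expected. Patients who later prove to have ACS are not excluded.
- **Instrumentation-Data collection** has two medication items. One is "confirmation with the patient that they are not on anti-platelet medicines", with a list of antiplatelet agents and no anticoagulant. The other is "We will record time and dosing of aspirin administration, time and dosing of narcotic medicines". The medical record number is kept in the study spreadsheet.
- **Research Design** states that "The treating clinician will determine the appropriate pain treatment plan for each patient".
- **Data Analysis Procedure** states that "Two-tailed T-testing will be used to look for differences in the 2 hour platelet reactivity response rates", comparing each narcotic group with the no-narcotic group. It plans no adjustment and no sensitivity analysis.
- **Theoretical Framework** describes antiplatelet treatment of ACS as "commonly including dual anti-platelet therapy with clopidogrel as well".

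**The concern.** The protocol names a confounder and then appears to measure only half of it. Prior use is screened out, but a drug begun in the department after the first draw is neither excluded nor recorded. The groups are not randomised. A patient whose presentation worries the clinician might be more likely to get both a narcotic and early antithrombotic treatment. An imbalance would then sit inside the t-test, and the planned data would not show it.

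The hypothesis is that narcotics blunt aspirin, so that 2-hour aggregation is higher with a narcotic. If more narcotic patients also received a drug that lowers aggregation, part of that difference would be hidden. If such use were commoner without a narcotic, a difference could be created or enlarged. The documents do not say which is likelier. The apparent remedy is cheap: a few extra chart fields and one sensitivity analysis.

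**Working it through.** **1. What the confounding remark covers.** The sentence in Research Questions or Hypothesis is about ACS patients, and the same paragraph answers it by changing the population. The exclusions then remove prior users. What remains is the subset of general chest-pain patients who start such a drug between the two draws. The documents give no size for this subset.

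**2. What limits the effect.**
- The 2-hour aggregation sample comes from the same draw as the second troponin (Methodology), so treatment prompted by that troponin comes after the outcome.
- Patients not expected to have a second troponin are excluded. By inference, this removes some who are moved quickly to other treatment.
- Methodology chooses arachidonic acid as the trigger because it follows aspirin's pathway, and says the stronger antiplatelets act elsewhere in the cascade.
- Theoretical Framework says of morphine: "Delayed onset of action or decreased absorption has also been demonstrated with stronger anti-platelet drugs such as clopidogrel". That would weaken any masking by an oral agent in the morphine group.

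**3. The planning figure.** Inputs from Data Analysis Procedure are means of 113 and 71, SDs of 94 and 66, alpha 0.05, power 0.80 (the text's beta of 0.8 read as power) and 80 per arm.

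- n per arm = 2 × (1.960 + 0.842)² × SD² / 42².
- With the mean SD, (94 + 66)/2 = 80, n = 57, the stated figure.
- With the root-mean-square SD, √((94² + 66²)/2) = √6596 = 81.2, n = 59.
- Standardised effect d = 42/81.2 = 0.517.
- Power of a two-sided t-test at 80 per arm = 0.902.

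This effect comes from an ADP/ticagrelor setting. It is used here as a yardstick for either narcotic comparison.

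**4. Size of the bias.** Bias in SD = (difference in use between groups) × (shift per treated patient in SD). Neither input is in the documents. The assumed ranges are 5 to 20 percentage points and 0.1 to 0.5 SD.

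| Case | Use difference × shift | Bias (SD) | Share of 0.517 | Power if masking | Two-sided error if no true effect |
|---|---|---|---|---|---|
| No bias | – | 0 | 0% | 0.902 | 0.050 |
| Low | 0.05 × 0.1 | 0.005 | 1% | 0.896 | 0.0501 |
| Middle | 0.10 × 0.25 | 0.025 | 5% | 0.872 | 0.0528 |
| High | 0.20 × 0.5 | 0.10 | 19% | 0.746 | 0.0964 |

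On the planning scale the middle case is 0.025 × 81.2 = 2.0 units against a planned difference of 42.

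**5. When it would matter.** Power falls to 0.80 at a bias of 0.0715 SD (0.0715 × 81.2 = 5.8 units).

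- At a shift of 0.5 SD this needs a use difference of 0.0715/0.5 = 14.3 points, or 11.4 of 80 patients.
- At 0.25 SD it needs 0.0715/0.25 = 28.6 points, or 22.9 of 80, which is outside the assumed range.

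**6. What a sensitivity analysis would give.**
- Excluding users, with 5%, 10% or 20% use in both groups, leaves 76, 72 or 64 per arm. Power at d = 0.517 is 0.886, 0.869 or 0.827.
- Adjusting keeps everyone. With 0% against 5% use, the correlation of group with drug is 0.160, the variance inflation 1/(1 − 0.160²) = 1.026 and power 0.894. With 0% against 20%, the figures are 0.333, 1.125 and 0.865.

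The loss of precision is modest. The difficulty is interpretation. The drug is given after baseline, possibly in response to how the patient fares after the narcotic, so excluding or adjusting on it can introduce a bias of its own. With few users it would also say little.

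**The case for a change.** The strongest case for a change is that the protocol redesigned its population around this confounder and should be able to show how much of it remains. The arachidonic-acid argument is incomplete: Methodology does not say that stronger antiplatelets leave the result unchanged, and it says nothing there about anticoagulants, the class named as confounding. Every participant is having serial troponins, so some will prove to have ACS. Analyses chosen after the data are seen carry less weight than those written down beforehand.

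Larger shifts also give larger harm. Take a 20-point imbalance and a shift of 71 units per treated patient. The bias is 0.20 × 71 = 14.2 units, power falls to about 58%, or error rises to about 20% (normal approximation).

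Part of this stands. The field is missing, and a count of such drugs by group would be useful to a reader. The extreme figures carry little weight: 71 units is the whole no-fentanyl mean in the cited trial, and they need the largest imbalance at the same time. The loss from not pre-specifying is also small, because the only firm product is descriptive. The coordinator already reads each chart for aspirin and narcotic times, and the record number is kept, so the count can probably be retrieved later.

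**Conclusion.** The omission is a matter of reporting detail, and the plan need not change. The confounding statement was made about ACS patients and was met by the choice of population and the exclusion of prior users. What is left is a subgroup of unknown size, sampled at the second-troponin draw with a trigger chosen for aspirin's pathway.

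In the middle assumed case (a 10-point difference in use and a 0.25 SD shift), power falls from 90% to 87% and two-sided error rises from 5.0% to 5.3%. Power drops below 80% only with about a 14-point imbalance at the largest assumed shift. These sizes rest wholly on assumed inputs and on a planning effect from a different drug and trigger.

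The primary comparison and the 80 per arm would be the same with the extra fields. The added analysis would condition on a post-baseline drug and could mislead as easily as reassure. A count by group is sensible practice that the study team can supply from the charts. The wider matter of unadjusted t-tests on clinician-chosen groups is a separate question. This is one small example of it and does not call for its own rule.
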